#### 2.5. **Good Clinical Practice (GCP)**

The principal investigator will ensure that the basic principles of GCP, as outlined in 21 Code of Federal Regulations (CFR) 312, subpart D, "Responsibilities of Sponsors and Investigators," 21 CFR, Part 50 (1998) and 21 CFR, Part 56, (1998) are followed.

Since this is a covered clinical trial, the principal investigator is adhered to 21 CFR, Part 54, (1998). A covered clinical trial is any "study of a drug or device in humans submitted in a marketing application or reclassification petition subject to this part that the applicant or FDA relies on to establish that the product is effective (including studies that show equivalence to an effective product) or that make a significant contribution to the demonstration of safety." This requires that investigators and all sub-investigators must provide documentation of their financial interest or arrangements with Epizyme, Inc. or proprietary interests in the drug being studied. This documentation must be provided prior to the participation of the principal investigator and any sub-investigator. The principal investigator and sub-investigator agree to notify Epizyme, Inc. of any change in reportable interests during the study and for one year following completion of the study. Study completion is defined as the date that the last subject has completed the protocol-defined activities.

# 3. STUDY OBJECTIVES AND ENDPOINTS

Objectives	Endpoints

 
Part 1 (Pharmacokinetics)
 
To assess the PK and safety profile of single and repeated doses of 800 mg tazemetostat administered as 400 mg tablets to subjects with relapsed or refractory malignant mesothelioma regardless of BAP1 status
 
Part 2 (Efficacy)
 
To assess disease control rate (DCR) at 12 weeks (consisting of complete response [CR], partial response [PR], or stable disease [SD]) according to modified RECIST [Nowak, 2005] for thoracic disease or RECIST 1.1 elsewhere in subjects with relapsed or refractory BAP1-deficient malignant mesothelioma treated with tazemetostat
 
	
 
AEs and clinical laboratory tests
 
Cmax, Tmax, AUC0-t, AUC0-∞ (single dose only), and t1/2 of tazemetostat after administration as 400-mg tablets.
 
DCR (CR+PR+SD) at Week 12
 

 
Secondary
 
Parts 1 and 2
 
To assess the safety and tolerability of tazemetostat
 
To assess the overall response rate (ORR) in subjects with relapsed or refractory malignant mesothelioma treated with tazemetostat
 
To determine the progression-free survival (PFS) and OS at 12 weeks, 24 weeks, and overall in subjects with relapsed or refractory malignant mesothelioma treated with tazemetostat
 
	
 
AEs and clinical laboratory tests
 
ORR (confirmed CR+PR) to tazemetostat in subjects with relapsed/refractory malignant mesothelioma using disease-appropriate standardized response criteria (modified RECIST or RECIST 1.1)
 
PFS at 12 weeks, 24 weeks, and overall (defined as the time from date of first dose of study treatment to the earlier of the date of first documented disease progression or date of death due to any cause)
 
OS at 12 weeks, 24 weeks, and overall (defined as the time from the date of the first dose of study treatment to the date of death due to any cause)
 

Objectives	Endpoints		
To evaluate the duration of response (DOR) in subjects with relapsed or refractory malignant mesothelioma treated with tazemetostat      Part 1	DOR, for the subset of subjects with a confirmed CR or PR (defined as the time from the first documented evidence of CR or PR to the time of first documented disease progression or death due to any cause, using disease-appropriate standardized response criteria)		
To assess DCR at 12 weeks (consisting of CR, PR, and SD) in subjects with relapsed or refractory malignant mesothelioma treated with tazemetostat	DCR (CR+PR+SD) at Week 12		

 
Part 2
 
To assess the population PK parameters of tazemetostat
 
To investigate the PD effects of tazemetostat in tumor tissue before and after treatment with tazemetostat (optional)
 
	
 
Population PK parameters oral clearance (CL/F), oral volume of distribution (Vd/F), and first-order absorption rate constant (Ka) for tazemetostat
 
Changes in H3K27me3 levels between pre- and post-dose tumor tissue
 
		
Exploratory			
Parts 1 and 2			
To explore the relationship between plasma PK and tumor PD markers	Tumor target gene expression and phenotypic markers including those for differentiation, apoptosis, inflammation and cell proliferation and their correlation with activity		
To assess tumor tissue and blood for somatic mutations, germline variants, messenger ribonucleic acid (mRNA), and/or proteins as candidate markers or response to tazemetostat	Somatic mutation analysis of tumor tissue and blood derived circulating deoxyribonucleic acid (DNA)		

## 4. STUDY DESIGN

#### 4.1. Study Sites

This study will be conducted at 6 - 10 sites in the US and 3 - 4 sites each in France and the United Kingdom.

### 4.2. Overview of Study Design

This is a Phase 2, multicenter, open-label, 2-part, single-arm, 2-stage study of tazemetostat 800 mg BID administered orally. Screening of subjects to determine eligibility for the study will be performed within 21 days of the first planned dose of tazemetostat.

In Part 1, 12 subjects with relapsed or refractory malignant mesothelioma regardless of BAP1 status will be treated and undergo PK blood sample collection after a single tazemetostat 800 mg dose on Cycle 1 Day 1 and on Cycle 1 Day 15 after repeated BID doses of tazemetostat 800 mg. Subjects will receive a single oral 800-mg tazemetostat dose on Cycle 1 Day 1. Starting on Cycle 1 Day 2, tazemetostat will be orally administered at a dose of 800 mg BID.

Part 2 will include subjects with BAP1-deficient relapsed or refractory malignant mesothelioma. Subjects will receive orally administered tazemetostat 800 mg BID starting on Cycle 1 Day 1. A two-stage Green-Dahlberg design will be utilized with a stopping rule to allow early termination at the end of Stage 1 if there is strong evidence of lack of efficacy based on results from the first 30 treated subjects who meet the criteria outlined below. If early stopping criteria are met, enrollment will be stopped. To avoid disruptions in the study, enrollment and treatment of subjects will not be halted in order to conduct the interim analysis.

The interim analysis will be performed after the first 30 treated subjects enrolled have completed at least the 12-week assessment, completed the final study visit or terminated early from the study, whichever is sooner. This is to ensure subjects have adequate time to respond to treatment. As it is desirable to perform the interim analysis in a timely manner, both confirmed and unconfirmed responses will be included.

The interim analysis planned at the end of Stage 1 may occur sooner if the Stage 1 rejection criterion is surpassed before all 30 subjects are treated and followed for 12 weeks. In this scenario, the total sample size (Stage 1 + Stage 2) would still remain unchanged at 55 subjects.

Treatment with tazemetostat will continue until disease progression, unacceptable toxicity or withdrawal of consent, or termination of the study. Response assessment will be evaluated after 6 weeks of treatment and then every 6 weeks thereafter while on study.

Subjects also will undergo physical examinations (PEs); vital sign measurements; ECOG assessments, blood sample collection for hematology, chemistry, PK, and PD markers; electrocardiograms (ECGs); adverse event (AE) assessments; concomitant medication assessments; activity assessments, and pregnancy testing for females of childbearing potential.

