### Statistical methods

**Sample size rationale:** The sample size of 12 subjects for Part 1 is sufficient for an initial assessment of the PK and safety profiles of the 400-mg tablet. The sample size in Part 2 is calculated on the primary endpoint using a two-stage Green-Dahlberg design. The hypothesis will be tested using a one-sided test with  $\alpha$ =0.05 and the type II error rate will be controlled at 0.2.

Null Hypothesis: CR + PR + SD at 12 weeks  $\leq 20\%$ Alternative Hypothesis: CR + PR + SD at 12 weeks  $\geq 35\%$ 

Green-Dahlberg	CR + PR + SD at 12 weeks
Stage 1 Sample Size (n1) a	30
Stage 1 Rejection of Drug (r1) a	4
Maximum Sample Size (n)	55
Stage 2 Rejection of Drug (r)	16

a. The interim analysis planned at the end of Stage 1 may occur sooner if the Stage 1 rejection criterion is surpassed before all 30 subjects are treated and followed for 12 weeks. In this scenario, the total sample size (Stage 1 + Stage 2) would still remain unchanged at 55 subjects.

- At the End of Stage 1, if there are ≤4 CR + PR + SD out of 30 subjects, then reject the new treatment and terminate the study for futility. If there are ≥5 CR + PR + SD out of 30 subjects, the study continues to Stage 2.
- At the end of the study, if there are ≤16 CR + PR +SD out of 55 subjects, then reject the new treatment. When there are ≥17 CR + PR + SD out of 55 subjects, then the new treatment is accepted.
- The probability of early stopping under the null hypotheses is 0.255.
- The probability of early stopping under the alternative hypotheses is 0.008.

**Table 1:** Study Assessments

	Screening a	Cycle 1	Cycle 1	Cycles 2 – 8	Cycles 9 +	Post- Treatment/ Early Termination q	Follow-up r
Study Days	Days -21 to -1	Day 1	Days 8 & 15 (±1 day)	Day 1 & every 21 days (±3 days)	Day 1 & every 42 days (±3 days)	(±3 days)	
Procedures/Assessments b							
Informed consent	X						
Inclusion/exclusion criteria c	X	X					
Demographics	X						
Medical History	X						
Prior and concomitant medications				Throughout the	study		
Physical examination - Complete	X	X		X	X	X	
Physical examination - Symptom directed			X				
Weight	X	X		X	X	X	
Height	X						
Vital signs d	X	X	X	X	X	X	
ECOG performance status	X	X	X	X	X	X	
12-lead ECGs e	X	X	X	X	X	X	
Pregnancy test f	X	X		X	X	X	
Hematology g	X	X	X	X	X	X	
Blood chemistry g	X	X	X	X	X	X	

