# 10.2. Survival Follow-Up

Subjects who permanently discontinue study treatment will be followed (by phone, email or clinic visit) for survival every 12 weeks until death, withdrawal of consent, or lost to follow-up.

Survival follow-up will continue until 80% of treated subjects have died. At such time, the subjects who are continuing on study treatment and have received 12 months of treatment on the current study will be followed and treated on a subsequent extension study.

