## 10.5. Withdrawal of Subjects from Study

Withdrawal of full consent for a study means that the subjects does not wish to receive further protocol-required treatment, procedures and does not wish to or is unable to continue further study participation. Subject data up to withdrawal of consent will be included in the analysis of the study, and where permitted, publicly available data can be included after withdrawal of consent (e.g., death records). The investigator must document this agreement regarding withdrawal of full consent as well as discuss appropriate procedures for withdrawal from the study.

Reasons for removal of a subject from the study might include the following:

- Death
- Decision by sponsor to terminate the study
- Subject request to withdraw from study
- Lost to follow-up

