### 13.2. Study Design Considerations

### **13.2.1** Determination of Sample Size

The sample size of 12 subjects for Part 1 is sufficient for an initial assessment of the PK and safety profiles of the 400 mg tablet.

For Part 2 of the study, evaluation will be done using a Green-Dahlberg two-stage design, to allow early termination of the study due to the lack of efficacy. The sample size is calculated on the primary endpoint. The hypothesis will be tested using a one-sided test with  $\alpha$ =0.05 and the type II error rate will be controlled at 0.2. The numbers of subjects to be enrolled using a Green-Dahlberg two-stage design is listed in the table below.

Green-Dahlberg	CR + PR + SD at 12 Weeks
Stage 1 Sample Size (n1)	30
Stage 1 Rejection of Drug (r1)	4
Maximum Sample Size (n) a	55
Stage 2 Rejection of Drug (r)	16

CR = complete response; PR = partial response; SD = stable disease a. The interim analysis planned at the end of Stage 1 may occur sooner if the Stage 1 rejection criterion is surpassed before all 30 subjects are treated and followed for 12 weeks. In this scenario, the total sample size (Stage 1 + Stage 2) would still remain unchanged at 55 subjects.

Approximately 30 subjects will be enrolled and treated in Stage 1 (see Section 13.3.2, Interim Analyses, for further details). While evaluating the response for the first 30 treated subjects, the enrollment and treatment of subsequent subjects will be continued. If the study continues on to Stage 2, a total of 55 subjects will be enrolled in the entire study.

- The probability of early stopping under the null hypotheses is 0.255.
- The probability of early stopping under the alternative hypotheses is 0.008.

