### 13.3. Data Analysis Considerations

### 13.3.1 Analysis Populations

The Intent-to-Treat (ITT) population will consist of all subjects who receive at least one dose of tazemetostat. The ITT population will be used for summaries and analysis of the efficacy endpoints.

The **Safety Population** will consist of all subjects in the ITT population who have at least one post-dose safety observation recorded. The Safety Population will be used for summaries and analysis of the safety and tolerability.

The **Pharmacokinetic** (**PK**) **population** set will include all subjects in the ITT population who have sufficient post-dose samples collected to allow estimation of the PK parameters. The PK population will be used for PK analysis.

The **Pharmacodynamic (PD) population** will include all subjects in the ITT population who have sufficient samples collected to allow estimation of the PD parameters. The PD population will be used for summaries and graphs of PD data.

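### After a Stage 1 futility stop, Part 2 subjects dosed after the 30th may be scored as disease-control failures because termination cancelled their Week 12 scan; this lowers the reported DCR but not the decision (minor, cheap to fix)

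*Combined protocol and SAP*

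**What the plan says.** Part 2 continues accrual during the interim. Section 4.2: "enrollment and treatment of subjects will not be halted in order to conduct the interim analysis". Section 13.2.1: "While evaluating the response for the first 30 treated subjects, the enrollment and treatment of subsequent subjects will be continued". The total is capped at 55, so up to 25 subjects beyond the first 30 may have been dosed when the futility result is known.

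The consequence of 4 or fewer controlled of 30 is worded in two ways. The Synopsis (Statistical methods) and 13.3.2 say "then reject the new treatment and terminate the study for futility". Section 4.2 describes the rule as allowing early termination, but the action it names is narrower: "If early stopping criteria are met, enrollment will be stopped".

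Scans are tied to being on study: "Response assessment will be evaluated after 6 weeks of treatment and then every 6 weeks thereafter while on study" (4.2). Section 10.5 gives, among possible reasons for removing a subject from the study, "Decision by sponsor to terminate the study". Section 10.2 covers survival only: "Survival follow-up will continue until 80% of treated subjects have died".

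On analysis, 13.3.1 says the ITT "population will consist of all subjects who receive at least one dose of tazemetostat", and this is the set for efficacy. Under 13.4.1 the primary cut-off is met by a Week 12 assessment, a final visit or early termination. A missing or non-evaluable response counts as not controlled and stays in the denominator. The DCR is reported with an exact 90% CI.

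**The concern.** Counting a missing Week 12 response as failure suits progression, death or dropout; the example in 13.4.1 is progression or death before Week 12. It does not suit a subject whose Week 12 visit never fell due because the sponsor ended the study.

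If the Synopsis and 13.3.2 govern and response assessments end with the study, a subject dosed after the 30th and not yet at Week 12 meets the cut-off by early termination, stays in the efficacy set and is scored as not controlled. If only enrollment stops, the scans remain due and there is no problem. The passages do not settle what happens to subjects already dosed.

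At stake is the primary estimate and interval published after a stop. They would be lower than the data support, and the interval could exclude 20% only because unobserved subjects were entered as failures.

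**Working it through.** **Inputs from the protocol.** n1 = 30, stop at 4 or fewer, maximum 55 (Synopsis, 13.2.1, 13.3.2); null DCR 20%, alternative 35% (13.1); exact 90% CI (13.4.1).

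**Assumptions.** The documents give neither the accrual rate nor the lag L (in weeks) from the 30th subject's Week 12 to the stop. With 4.35 weeks per month:
- dosed past the 30th: m = min(25, rate × (12 + L)/4.35), rounded;
- of these, reached Week 12: k = rate × L/4.35, rounded.

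L = 0 gives m = 3, 8, 17, 25 at 1, 3, 6, 9 per month, with k = 0. L = 4 gives m = 4, 11, 22 and k = 1, 3, 6 at 1, 3, 6 per month.

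**Step 1: the plan's own figures.** P(X ≤ 4) for X ~ Bin(30, p) is 0.2552 at p = 0.20 and 0.0075 at p = 0.35. These match the stated 0.255 and 0.008.

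**Step 2: the estimate at the boundary.** Clopper-Pearson 90% limits are the 0.05 quantile of Beta(x, n − x + 1) and the 0.95 quantile of Beta(x + 1, n − x). With 4 controlled in the first 30 and m later subjects all entered as failures (k = 0):

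| m | DCR | exact 90% CI |
|---|---|---|
| 0 | 4/30 = 13.3% | 4.7-28.0% |
| 3 | 4/33 = 12.1% | 4.2-25.6% |
| 8 | 4/38 = 10.5% | 3.7-22.5% |
| 25 | 4/55 = 7.3% | 2.5-15.9% |

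**Step 3: the average after a stop, true DCR 20%.** Given X ≤ 4, the probabilities of 0, 1, 2, 3, 4 are 0.005, 0.036, 0.132, 0.308, 0.519, so the mean is 0.036 + 0.264 + 0.924 + 2.076 = 3.30. On the first 30 the mean DCR is 3.30/30 = 11.0%. This is already well below 20%, because it is selected on stopping. With later subjects not at Week 12 entered as failures, the mean is (3.30 + 0.2k)/(30 + m):

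| L | m (k) | mean DCR |
|---|---|---|
| 0 | 3 (0) | 3.30/33 = 10.0% |
| 0 | 8 (0) | 3.30/38 = 8.7% |
| 0 | 17 (0) | 3.30/47 = 7.0% |
| 0 | 25 (0) | 3.30/55 = 6.0% |
| 4 | 4 (1) | 3.50/34 = 10.3% |
| 4 | 11 (3) | 3.90/41 = 9.5% |
| 4 | 22 (6) | 4.50/52 = 8.7% |

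Against 11.0%, the no-lag shortfall is 1.0, 2.3, 4.0 and 5.0 points.

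**Step 4: chance that the CI excludes 20% after a stop, true DCR 20%.** On the first 30 alone the upper limit is 0.1953 at 2/30 and 0.2386 at 3/30. At 3 controlled it falls below 0.20 between 3/36 (0.2015) and 3/37 (0.1964); at 4 controlled, between 4/43 (0.2004) and 4/44 (0.1961).

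If no later subject reached Week 12:
- m = 0-6: P(X ≤ 2 | stop) = 0.17;
- m = 7-13: P(X ≤ 3 | stop) = 0.48;
- m = 14-25: 1.00.

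If k of them reached Week 12, add Y ~ Bin(k, 0.2) to X. The largest total that excludes 20% is 2 of 34, 3 of 41 and 5 of 52. The chances are:
- m = 4, k = 1: 0.15;
- m = 11, k = 3: 0.32;
- m = 22, k = 6: 0.79.

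**The case against.** **The wordings can be read together.** Section 4.2 itself speaks of early termination, so stopping enrollment may be just the operational step. No section says that dosed subjects are removed at a futility stop; 10.5 only lists sponsor termination as something that might apply. This stands to the extent that the problem is conditional. A reader might infer that these subjects would certainly lose their scans, and the documents do not say so.

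**Follow-up may continue.** Section 7.7 provides follow-up to at most 12 months from first dose when treatment ends early, and Table 1 marks a disease assessment and survival status row at the post-treatment and follow-up visits. Neither guarantees a Week 12 scan: 7.7 names no imaging, and the Table 1 footnote to that row describes only survival contact about every 12 weeks.

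**A rule exists.** A reader might infer that the plan is silent on these subjects. It is not: the general missing-response rule in 13.4.1 reaches them, and it is what produces the bias. What is missing is a specific rule for visits precluded by study termination. Section 13.3.3 leaves full details to an SAP and Section 14 leaves the interim plan to an IDMC charter; neither separate document is in the text supplied, so such a rule may exist there.

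**The consequence is small.** The drug has already been rejected on a count out of 30, and that count can be reported whatever the all-treated rate. At 4/30 it takes 14 added subjects before the interval excludes 20%. This stands, and it is why the point is minor.

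**Conclusion.** The point holds as a minor one about reporting. If a futility stop ends response assessments, the stated rules count subjects never due a Week 12 scan as failures, and the primary DCR and its 90% CI are biased downward. With no lag and a true DCR of 20%, the mean reported DCR falls from 11.0% on the first 30 to between 10.0% (3 added) and 6.0% (25 added). With few added subjects the effect is about one point.

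The size rests on assumed accrual and lag, and on 13.3.2 rather than the narrower action in 4.2 being applied. Subjects who had reached Week 12, progressed or died before the stop are scored correctly as it is.

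Three stronger inferences are not supported:
- That the trial's decision or error rates are compromised. Futility uses only the first 30, and the 17-of-55 rule is not applied after a stop.
- That 14 or more added subjects always make the CI exclude 20%. This is so only if none of them reached Week 12; with 22 added and 6 at Week 12 the chance is 0.79.
- That the first-30 result is an unbiased standard. It averages 11.0% when the truth is 20%, through selection on stopping; the failure scoring adds a further, avoidable shift.

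**What to change.** 1. Reconcile 4.2 with 13.3.2 and the Synopsis on what a futility stop means for subjects already dosed. The sponsor decides which applies.
2. State in 13.3.2 and 13.4.1 that, after a futility stop, a subject whose Week 12 assessment was precluded by study termination is not scored as a failure.
3. If later subjects are not followed to Week 12, report the DCR and exact 90% CI on the first 30 treated, with a note that this estimate is selected on stopping. List later subjects separately by status: Week 12 result available; progressed or died before Week 12; Week 12 not reached because the study stopped. Give the all-treated DCR as a sensitivity analysis.
4. If they are followed to Week 12, keep the all-treated DCR under 13.3.1 and also report the first-30 DCR on which the decision was made.

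The cost is one reconciled phrase, a few sentences and one extra table after a stop. Sample size and boundaries do not change. Setting the rule before the interim avoids choosing a denominator after the data are seen.

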# 4.3. Rules for Suspension of Enrollment

The investigators, IRBs/ECs, regulatory agencies and IDMC will be urgently informed and the IDMC convened to review the data and to make recommendations for potential changes in study conduct if one or more subjects develop any of the following AEs deemed to be definitely related to study treatment by the investigator and/or medical monitor, based upon close temporal relationship or other factors:

- Death
- Anaphylaxis (angioedema, hypotension, shock, bronchospasm, hypoxia or respiratory distress)
- Secondary lymphoma

Should study enrollment be suspended, the study will not be restarted until all parties have agreed to the course of action to be taken and the IRBs/ECs have been notified.

